10.2.2 AE summaries

Summary tables with the number, percentage of study participants and frequency of TEAEs will be provided by treatment group and RLZ total. Additional details are as follows:

1. Overview of TEAEs will include following categories: any TEAEs, serious TEAEs, participant discontinuation due to TEAEs, permanent withdrawal of IMP due to TEAEs, temporary withdrawal of IMP due to TEAEs, treatment-related TEAEs, severe TEAEs, TEAEs leading to death, all deaths (AEs leading to death).
2. Incidence of TEAEs will be summarized by SOC, HLT and PT for:
 - Any TEAEs
 - TEAEs during Treatment Period
 - Severe TEAEs
 - Any TEAEs by maximum intensity (mild, moderate and severe)
 - Any TEAEs by relationship
 - Any TEAEs relative to ADA status
 - Any TEAE by Risk Difference $\geq 5\%$ (by decreasing frequency of Risk Difference)
 - Non-serious TEAEs above reporting threshold of 5% of study participants
 - Fatal TEAEs
 - Fatal TEAEs by relationship
 - Serious TEAEs
 - Serious TEAEs by relationship
 - Participant discontinuation due to TEAEs
 - TEAEs leading to permanent withdrawal of IMP
 - TEAEs leading to temporary withdrawal of IMP
 - Treatment-emergent AESM
 - Treatment-emergent AESI
3. Incidence of TEAEs will be summarized by PT for:
 - Any TEAEs by decreasing frequency of PT

AESMs include severe headache, severe GI disorders (i.e., abdominal pain, diarrhea, vomiting), and opportunistic infection.

AESIs are the cases of potential Hy's Law (see [Section 10.3.1](#)).

AESMs and AESIs will be identified based on the assessment by the Investigator as recorded in the CRF. An AE will be counted as an AESM if there is a 'yes' response to the question "Adverse event of Special Monitoring?" and 'no' otherwise. An AE will be counted as an AESI

if there is a ‘yes’ response to the question “Adverse Event of Special Interest?” and ‘no’ otherwise.

When applicable adverse event summaries will be ordered by alphabetical SOC, alphabetical HLT within SOC and decreasing frequency of PT in the rozanolixizumab total column for tables.

Listings of all TEAEs, all non-serious TEAEs, serious TEAEs, permanent withdrawal of IMP due to AEs, study participant discontinuation from study due to AEs, AEs leading to death, AESIs, AESMs will be presented by treatment group and study participants.

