active for MG0007, no further participants will enroll in MG0004 and the study will be closed at the site once all eligible study participants have discontinued MG0004 and had the opportunity to rollover into MG0007.

The maximum duration of the study per study participant will be up to 18 weeks, consisting of a Screening Period (1 to 28 days to account for central laboratory turn-around time), a Treatment Period (6 weeks), and a blinded Observation Period (8 weeks).

1. All study participants who complete the 6-week Treatment Period will roll over into an 8-week Observation Period.
2. All eligible study participants who complete the Observation Period will be invited to be re-randomized into an OLE study to either active dose arm 1 or 2.
3. Study participants who experience disease worsening during the 6-week Treatment Period (eg, an increase of 2 points on the MG-ADL or 3 points on the QMG scale between two consecutive visits) may be considered for rescue therapy (IVIg or PEX) at the discretion of the Investigator.
4. Study participants who need rescue therapy during the 6-week Treatment Period will receive IVIg or PEX and complete any subsequent visit(s). No further infusions of rozanolixizumab will be administered after initiation of rescue therapy. Once the participant completes Visit 10, he or she will move into the 8-week Observation Period.
5. Study participants who complete the Treatment Period and require initiation of rescue therapy after they start the 8-week Observation Period, may either opt to receive IVIg or PEX or complete the EOS visit and immediately roll over into an OLE study where the participant will receive rozanolixizumab. Study participants who opt to receive IVIg or PEX will complete any remaining visits in the Observation Period and will not be invited to join an OLE study.
6. Study participants who did not complete the 6-week Treatment Period because they needed rescue therapy and require initiation of a second course of rescue therapy while in the 8-week Observation Period can roll over to an OLE study if a minimum of 2 weeks have lapsed since completion of the last IVIg or PEX session. The EOS visit must be completed before enrolling into an OLE study. Alternatively, they can be treated with IVIg or PEX. Study participants who opt to receive IVIg or PEX will complete any remaining visits in the Observation Period and will not be invited to join an OLE study .

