10.2 Adverse events

10.2.1 Data considerations

Adverse events will be recorded from the time of informed consent until study completion. All AEs will be coded ([Section 3.8](#)).

In addition, AEs will be classified according to the Common Terminology Criteria for Adverse Events (CTCAE) Version 5 or later for severity. For any AEs where it is not possible to provide a CTCAE grading, the events will be assessed using a standard intensity classification (mild,

moderate and severe). For the purpose of the tabulations all CTCAE severity classifications will be mapped to a mild/moderate/severe grade as described below:

- Grade 1-- Mild
- Grade 2-- Moderate
- Grade 3, 4, 5-- Severe

These will be tabulated together with the AEs that were not classified according to CTCAE criteria i.e., all Grade 1 AEs as per CTCAE criteria will be included in the 'mild' category together with those AEs classified as mild as per the 'standard' intensity classification. In the case a mapped standard intensity classification per above rule is different from the standard intensity classification on CRF, the worst case will be used as the standard intensity classification (i.e. an AE with Grade 1 and moderate as intensity classification will be classified into moderate).

A TEAE is defined as an AE starting on or after the time of first administration of IMP up to and including 8 weeks (56 days) after the final dose. Adverse events starting before the date of the first administration of IMP or after 8 weeks following the final dose of IMP will not be considered TEAEs. Thus AEs before first dosing and AEs after 8 weeks following the final dose will be combined in one category. Such events will be listed only.

Where dates are missing or partially missing, AEs will be assumed to be treatment-emergent unless evidence exists that does not allow the AE to be treatment-emergent. Handling of missing dates for classification of AEs as TEAEs is described in [Section 4.2.2](#).

The following rules will be used to assign a TEAE to a study period:

- **Treatment Period:** a TEAE will be assigned to the Treatment Period for the tabulations if the start date of the event is on or after the date of the first administration of IMP on Day 1, up to 7 days following the final dose of IMP

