- **Observation Period:** a TEAE will be assigned to the Observation Period for the tabulations if the start date of the event is greater than 7 days after the date of the final dose of IMP until 8 weeks following the final dose; events starting later than 8 weeks following the final dose of IMP are not considered TEAEs

In the case of early withdrawal in the Treatment Period, a TEAE will be assigned to the Treatment Period based on the last received IMP plus 168 hours (7 days). Subsequent TEAEs (up to 8 weeks post-last dose) will be assigned to the Observation Period.

A TEAE will be counted as a TEAE related to IMP if the response to the question "Relationship to Study Medication" is "Related". Severe TEAEs are those with CTCAE Grade 3 or above, or those without a CTCAE grading classified as 'severe' by the Investigator.

Es will be presented as "number of study participants (percentage of study participants) [number of events]". In this style of output, "[number of events]" will include all cases of an AE including repeat occurrences in individual study participants, while "number of study participants" will count each study participant only once.

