10.2.3 Adverse Events of Focus

Rozanolixizumab treatment-emergent adverse events of Focus (TEAEof) include the following categories:

- Headaches
- Gastrointestinal disturbances
- Hypersensitivity reactions
- Anaphylactic reactions
- Injection site reaction
- Infusion reaction
- Opportunistic infections
- Reductions in albumin and plasma proteins
- Effects on the kidney
- Drug related hepatic disorders

A by-subject listing of all treatment-emergent AEOF by category (as listed above) will be provided. The number and percentage of study participants who experience each treatment-emergent AEOF will be summarized by most recent dose level prior to onset of AEOFs and total Rozimab treatment group. The following summaries will be presented by SOC, HLT, and PT:

- Treatment-emergent AEOF
- Serious Treatment-emergent AEOFs
- Treatment-emergent AEOFs by relationship
- Treatment-emergent AEOFs by maximum intensity (mild, moderate and severe)
- Treatment-emergent AEOF hypersensitivity reactions, anaphylactic reactions and infusion reactions by ADA
- Treatment-emergent AEOF headache and GI disturbances in Treatment period by intensity
- Treatment-emergent AEOFs by Risk Difference (by decreasing frequency of Risk Difference)

Graphs for treatment-emergent AEOF headache by time of onset (relative to infusion), severity, causality and duration for each study participant will also be provided.

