13.8 AEs of focus for Rozanolixizumab program

The AEOF selection criteria is specified in the Rozimab Safety AEs of Focus document developed by UCB. The purpose of this document is to detail the approach to identifying TEAEs meeting criteria for AEOF for the Rozanolixizumab (also called Rozimab) program.

Following Events are AEOFs for Rozimab for MG studies:

No	Event (also included in Title of TFL output)	Selection criteria
1	Headache (Note: also included in AESM if severe)	TEAE with HLT='Headaches'
2	Gastrointestinal disturbances (Note: also included in AESM if severe)	TEAE with HLT='Gastrointestinal and abdominal pains (excl oral and throat)' or HLT='Gastrointestinal signs and symptoms NEC' or HLT='Nausea and vomiting symptoms' or HLT='Diarrhoea (excl infective)' or HLT='Gastritis (excl infective)'
3	Hypersensitivity reactions	SMQ='Hypersensitivity'
4	Anaphylactic reactions	SMQ='Anaphylactic reaction' and TEAEs that either emerged on the same day as when a study medication injection reaction was received, or that emerged one day after a study medication injection was received, and which fulfill any of the following 3 criteria should be included in the summary table:

		
 1. If a subject reports any TEAE which codes to a PT included in Category A, then the event will be flagged as an anaphylactic reaction. 2. If a subject reports any TEAE which codes to a PT included in Category B AND reports any TEAE which codes to a PT included in Category C, and both TEAEs have the same start date, then both events will be flagged as anaphylactic reactions. 3. If a subject reports any TEAE which codes to a PT included in Category D AND reports (either a TEAE which codes to a PT included in Category B OR a TEAE which codes to a PT included in Category C), and both TEAEs have the same start date, then both events will be flagged as anaphylactic reactions.
5	Injection site reactions	TEAE with HLT='Injection site reactions' or HLT='Infusion site reactions' or HLT='Administration site reactions NEC'
6	Infusion Reactions	Infusion reaction marked on AE CRF page (based on the assessment by the Investigator)

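### The serious, severe and several focus-event TEAE tables lack the Treatment Period version the SAP already defines, and SAEs starting after roll-over to open-label drug are not separated

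*SAP*

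**What the plan says.** SAP 10.2.1 counts an AE as treatment-emergent from the first IMP administration "up to and including 8 weeks (56 days) after the final dose". It then splits that window: "a TEAE will be assigned to the Treatment Period for the tabulations" if it starts within 7 days of the last dose, and to the Observation Period if it starts later. Tables show participants, percentages and event counts, with no time denominator.

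In SAP 10.2.2, "Summary tables with the number, percentage of study participants and frequency of TEAEs will be provided by treatment group and RLZ total". One item in the list that follows is limited to the Treatment Period: the incidence of any TEAE by SOC, HLT and PT. In SAP 10.2.3 the only such item is "Treatment-emergent AEOF headache and GI disturbances in Treatment period by intensity".

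Protocol 4.1 (item 5) gives a choice to a participant who completes treatment and then needs rescue in the Observation Period. One option is IVIg or PEX with the remaining visits. The other is to complete the EOS visit and "immediately roll over into an OLE study". Item 6 gives a similar exit to someone rescued during treatment who needs a second course, at least 2 weeks after the last session. SAP 5.1 plans a disposition sub-category for rescue-driven roll-over.

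Under Protocol 8.3.1, AEs are collected to the EOS visit, and SAEs are reported for a further 30 days whatever their cause. SAP 10.1 summarises weeks on IMP, not weeks under AE observation.

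**The concern.** A crude percentage compares arms fairly only if participants are observed for similar lengths of time. Here the exit is driven by need for rescue, which is itself an efficacy outcome that the SAP compares between arms (8.4.1). Observation time for non-serious AEs after Day 43 may therefore depend on treatment.

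SAEs raise a different problem. They are followed past EOS, so some may start after the participant has begun open-label rozanolixizumab and yet fall inside the 56-day TEAE window. The SAP has no rule that removes or marks them. A placebo participant's SAE on active drug could then appear in the placebo column.

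The affected tables bear on stated concerns: Protocol 2.3 names serious infections and serious infusion or hypersensitivity reactions as potential risks.

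**Working it through.** **1. Which tables already have an on-treatment view.**
- Any TEAE: yes, by SOC, HLT and PT (10.2.2).
- Headache and GI focus events: yes, by intensity (10.2.3). This also covers the severe headache and severe GI components of the AESM.
- Injection-site reactions: defined by HLT (13.8), so they can be read from the any-TEAE table.
- Anaphylactic reactions: limited in 13.8 to the day of an injection or the day after. Infusion reactions are tied to dosing by nature.
- Serious TEAEs, and severe TEAEs other than headache and GI: no. The any-TEAE table shows neither seriousness nor severity.
- Opportunistic infections: not as a group, because they rest partly on seriousness and physician adjudication (13.8).
- Hypersensitivity, renal and hepatic focus events: no. They are SMQ groupings.

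**2. Windows for a participant with all six doses.** The Schedule of Activities puts the last dose on Day 36.
- Treatment Period ends: 36 + 7 = Day 43.
- TEAE window ends: 36 + 56 = Day 92.
- Days after the Treatment Period: 92 − 43 = 49, or 49/92 = 53% of the window.

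**3. Early leavers.** Let w be the number of observation weeks completed, ignoring visit windows. EOS falls on Day 43 + 7w.

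| w | EOS day | Non-serious AE days lost (92 − EOS) | SAE reporting ends (EOS + 30) | Post-EOS SAE days inside window |
|---|---|---|---|---|
| 2 | 57 | 35 | 87 | 30 |
| 3 | 64 | 28 | 94 | 28 |
| 4 | 71 | 21 | 101 | 21 |
| 6 | 85 | 7 | 115 | 7 |

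The last column is the smaller of 30 and 92 − EOS. At w = 2 it is 30/92 = 33% of the window, and at w = 3 it is 28/92 = 30%. SAE reporting covers the whole window once 73 + 7w ≥ 92, that is from w of about 2.7. The two-week leaver is 92 − 87 = 5 days short. SAE follow-up is therefore nearly complete, and the issue for SAEs is attribution.

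**4. Attribution of those SAEs.** Protocol 8.3.1 requires them to be reported. SAP 4.2.2 has a date rule for AEs that start after discontinuation, so such records are foreseen. The 10.2.1 definition depends only on the time since the last dose, so it includes them. The reallocation rule in SAP 3.6 covers participants given the wrong treatment, not roll-over.

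**5. Limit of the Treatment Period itself.** Rescue during treatment stops IMP (Protocol 4.1, item 4), and SAP 10.2.1 then ends the Treatment Period 7 days after the last dose received. If IMP stops after the third dose on Day 15, that is Day 22, or 21 days earlier than Day 43. A Treatment Period table does not remove unequal follow-up from this source.

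**The case against.** Several counter-arguments carry weight.

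- **Attrition by arm will be visible.** SAP 5.1 counts participants at each visit by treatment group and reports Observation Period discontinuation. SAP 8.4.2 gives Kaplan-Meier time to first rescue with counts to Day 99. This stands. A summary of weeks under AE observation adds a direct figure, but the gain is small.
- **Much on-treatment content is already planned.** This also stands, and it narrows the request. Anaphylactic, infusion and injection-site tables need no second version, and Treatment Period risk differences can be read from the any-TEAE table. Listings would allow the rest to be rebuilt by hand, but that is not a prespecified comparison.
- **The full window has a pharmacological reason.** Protocol 4.2 sets the 8-week Observation Period to follow IgG recovery, so a cut at 7 days after the last dose omits part of the low-IgG period. This stands: the full-window tables must remain.
- **Open-label SAEs may never enter the MG0003 tables.** SAP 10.2.1 says AEs are recorded until study completion, and the extension protocols are not available. This stands in part. The documents do not say which database holds these SAEs, but the TEAE definition would count any that are in this one.

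A reader might also infer that an open-label dose decides the column of a focus event, since these events "will be summarized by most recent dose level prior to onset of AEOFs and total Rozimab treatment group". In a SAP confined to MG0003 that reading is strained, and the point does not depend on it.

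**Conclusion.** The point holds as a modest improvement in reporting. No planned analysis is wrong or impossible to run. What is missing is a Treatment Period view of the serious, severe, opportunistic-infection, hypersensitivity, renal and hepatic tables, and a rule for SAEs that start after roll-over.

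The dates above follow from the documents, assuming all six doses on schedule and open-label dosing soon after EOS. The effect on the arm comparison cannot be sized, because the plan gives neither exit rates nor AE rates by arm.

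Three stronger readings are not supported:
- A reader might infer that the full-window tables are biased in a known direction. The documents fix neither direction nor size.
- A reader might infer that worsening alone permits early exit. Protocol 4.1 requires a need for rescue therapy, and those who choose IVIg or PEX stay for the remaining visits.
- A reader might infer that Treatment Period tables would be free of unequal follow-up. Early stopping of IMP for rescue shortens that period too.

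**What to change.** 1. In SAP 10.2.2 and 10.2.3, add Treatment Period versions, using the 10.2.1 rule, of the serious and severe TEAE tables, the opportunistic-infection AESM/focus-event table, and the hypersensitivity, renal and hepatic focus-event tables. Keep all full-window versions.
2. In the full-window serious TEAE table and listing, flag SAEs that start after roll-over to open-label drug and show them separately from the count for the MG0003 arm.
3. In SAP 10.1, summarise weeks under AE observation by arm, for the Treatment Period and the full window. This also shows the shorter follow-up of participants who stop IMP early for rescue.

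The cost is SAP wording and a few more outputs. The period rule exists, and dose, onset and EOS dates are MG0003 data. For item 2, EOS with roll-over status can mark the switch if the first open-label dose date is not to hand. Sample size, power and alpha are unaffected.

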10.2.3 Adverse Events of Focus

Rozanolixizumab treatment-emergent adverse events of Focus (TEAEof) include the following categories:

- Headaches
- Gastrointestinal disturbances
- Hypersensitivity reactions
- Anaphylactic reactions
- Injection site reaction
- Infusion reaction
- Opportunistic infections
- Reductions in albumin and plasma proteins
- Effects on the kidney
- Drug related hepatic disorders

A by-subject listing of all treatment-emergent AEOF by category (as listed above) will be provided. The number and percentage of study participants who experience each treatment-emergent AEOF will be summarized by most recent dose level prior to onset of AEOFs and total Rozimab treatment group. The following summaries will be presented by SOC, HLT, and PT:

- Treatment-emergent AEOF
- Serious Treatment-emergent AEOFs
- Treatment-emergent AEOFs by relationship
- Treatment-emergent AEOFs by maximum intensity (mild, moderate and severe)
- Treatment-emergent AEOF hypersensitivity reactions, anaphylactic reactions and infusion reactions by ADA
- Treatment-emergent AEOF headache and GI disturbances in Treatment period by intensity
- Treatment-emergent AEOFs by Risk Difference (by decreasing frequency of Risk Difference)

Graphs for treatment-emergent AEOF headache by time of onset (relative to infusion), severity, causality and duration for each study participant will also be provided.

10.2.4 Safety analysis by weight subgroup and administered dose

To support the goal of a fixed dosing strategy for Rozanolixizumab, additional summary tables with the number, percentage of study participants and frequency of TEAEs (when applicable) will be provided by weight subgroup and administered dose and by SOC, HLT and PT for:

- Overview of TEAEs
- Incidence of TEAEs
- Incidence of Serious TEAEs
- Incidence of Severe TEAEs
- Incidence of AEOF of headache and GI disturbances
- Incidence of AEOF of headache and GI disturbances by maximum intensity (mild, moderate and severe)

10.3 Clinical laboratory evaluations

The following table (Table 10-1) lists safety laboratory assessments that are collected throughout the study:

Table 10-1: Clinical Laboratory Parameters

Laboratory Assessments	Parameters			
Hematology	Platelet Count	RBC Indices:		WBC Count with Differential:
	Red Blood Cell (RBC) Count	Mean corpuscular volume		Neutrophils
	Hemoglobin	Mean corpuscular hemoglobin		Lymphocytes
	Hematocrit	%Reticulocytes		Monocytes Eosinophils Basophils
Clinical Chemistry	Blood Urea Nitrogen (BUN)	Potassium	Aspartate Aminotransferase (AST)/ Serum Glutamic-Oxaloacetic Transaminase (SGOT)	Total and direct bilirubin
	Creatinine Estimated Glomerular	Sodium	Alanine Aminotransferase (ALT)/ Serum Glutamic-Pyruvic	Total Protein Albumin

Laboratory Assessments	Parameters			
	Filtration Rate (eGFR) ^a		Transaminase (SGPT)	
	Glucose (fasting state, preferred)	Calcium ^b	Alkaline phosphatase	C-reactive protein (CRP)
	Lactate dehydrogenase (LDH)	High-density lipoprotein (HDL) ^c	Total Cholesterol (TC)	Triglycerides (TRIG)
Routine Urinalysis	
 • Specific gravity • Albumin, albumin/creatinine, creatinine • pH, glucose, protein, blood, ketones, bilirubin, urobilinogen, nitrite, leukocyte esterase, hemoglobin by dipstick • Microscopic examination (if blood or protein is abnormal) 			
Other Screening Tests	
 • Serum or urine human chorionic gonadotropin (hCG) pregnancy test (as needed for women of childbearing potential)^d • PTT, INR, and HbA1c tests • Serology testing (for Hepatitis B, Hepatitis C, and HIV) 
All study-required laboratory assessments will be performed by a central laboratory.
 
 • The results of each test must be entered into the CRF. 			

NOTES:
 
All study-required laboratory assessments will be performed by a central laboratory.
 
The results of each test must be entered into the CRF.
 
^a eGFR is calculated using the Chronic Kidney Disease Epidemiology Collaboration (CKD-EPI) formula which is $eGFR = 141 * \min(Scr/\kappa, 1)^\alpha * \max(Scr/\kappa, 1)^{-1.209} * 0.993^{Age} * 1.018$ [if female] * 1.159 [if black]; where Scr is serum creatinine (mg/dL), κ is 0.7 for females and 0.9 for males, α is -0.329 for females and -0.411 for males, min indicates the minimum of Scr/κ or 1, and max indicates the maximum of Scr/κ or 1. If race is not captured, participant will be assumed not Black in the calculation.
 
^b Corrected Calcium (mmol/L) = $0.02 * (40 - \text{Albumin (g/L)}) + \text{Calcium (mmol/L)}$.
 
^c Calculation of Low-density lipoprotein (LDL) will follow Friedewald equation, where LDL in mmol/L = $TC - HDL - TRIG/2.22$; LDL in mg/dL = $LDL = TC - HDL - TRIG/5$ (if all values are in mg/dL). This formula is applicable only if Triglycerides is less than or equal to 400 mg/dL (4.52 mmol/L).
 
^d Local urine testing will be standard for the protocol unless serum testing is required by local regulation or Institutional Review Board (IRB)/ Independent Ethics Committee (IEC).
				

Chemistry, hematology and quantitative urinalysis (observed value, absolute change from Baseline) will be summarized in standard unit using descriptive statistics by treatment group and RLZ total at each scheduled visit.

The central data will be used for the summary tables. Measurements BLQ will be imputed with half of the lower limit of quantification LLOQ, and measurements ALQ will be imputed to the upper quantification limit for the purpose of quantitative summaries.

The number and percentage of study participants who meet each of the markedly abnormal (MA) criteria outlined in [Section 13.7](#) will be summarized by treatment group at any visit (including unscheduled visit).

The laboratory variables that are categorized as normal, high or low based on the reference range supplied by the analytical laboratory will be presented in shift tables from Baseline to any post-Baseline visit (including unscheduled visit) by treatment group.

Mean values in albumin, C-reactive protein and White Blood Cell Count with absolute count and differential (neutrophils, lymphocytes, monocytes, eosinophils and basophils) plotted over time by treatment, RLZ total with all treatments overlaid on the same plot. Lipids including High-density Lipoprotein, Low-density lipoprotein, Total Cholesterol, Triglycerides will be plotted the same way if data are available.

All laboratory test results will be listed, including Baseline, scheduled and unscheduled visits with results in standard unit. Values outside the reference range for the continuous variables will be flagged in the listings. The reference ranges will also be reported in the listings. In addition, the listings will include a flag for values identified as MA. Additional lab test, including pregnancy testing, will also be listed.

